18.4 Data Security

Limited study personnel will have access to study data stored on the institutional formsite account, and minimum password complexity requirements will be enforced, and recaptcha and two-factor authentication provide additional layers of security. Formsite servers are co-located in a cloud-based architecture with amazon web services (aws). All data stored on formsite are encrypted using the aes-256 encryption algorithm, and high-grade sha-256 rsa encryption is used for https connections over tls. Secure network access is enforced by multi-tiered firewalls, custom system configurations and multi-zones networks. [name], Center for Orthopaedic-Based

Outcomes, Director, manages institutional access to the TSC formsite account, and creates sub-user accounts that enable access to individual form(s) for specific research studies.

Standard of care patient questionnaire data is automatically exported from formsite.com onto The Steadman Clinic (TSC) server and into the TSC patient outcomes database. Upon successful transfer, questionnaire data is automatically deleted from formsite.com. Formsite uses secure “https” links by default for all patients that complete surveys, and no personally identifiable information (PII) is recorded through any website technologies on formsite.com.

18.5 Qualification of Study Staff

All study staff will be confirmed to be qualified as assigned to appropriately delegated study tasks. A Delegation of Authority Log will be kept at the study site in addition to documentation of applicable training and experience.

18.6 Training

Prior to initiating the study, all site personnel will undergo thorough training regarding the Protocol. Documentation of training will be retained at the study site.

18.7 Protocol Amendments

No changes in the study procedures shall be affected without mutual agreement of the Investigator and the applicable IRB. All protocol amendments must be documented in writing, including the date and justification for the change. All changes must be documented by signed protocol amendments, which will be submitted to the FDA as appropriate.

18.8 Handling of Study Medication

18.8.1 Dispensing and Labeling

Study Medication will be provided to the Vail Health Hospital Pharmacy in bulk by Vital Nutrients Compounding Pharmacy and will be stored in a secure location with limited access. Vail Health Hospital Pharmacy will fill prescriptions for each subject randomized. A prescription will be provided by the Study Team to the pharmacy indicating the appropriate randomization group and the number of pills to dispense.

The study medication label will contain the following elements: Protocol IRB #, PI Name, Name of Study Medication, Directions, and the statement, “Caution – New Drug Limited by Federal Law to Investigational Use.”

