3.0 Study Synopsis

Sponsor/ Investigator Sponsored Study	[name].
Study Title:	Senolytic Drugs Attenuate Osteoarthritis-Related Articular Cartilage Degeneration: A Clinical Trial
Protocol Number:	2019-16
Study Design:	Randomized, double-blind, placebo controlled
Study Duration:	Approximately 36 months Enrollment 18 months Follow-up 18 months
Randomization:	Subjects are to be assigned to one of two treatment groups using a 1:1 (Fisetin/placebo) randomization scheme.
Study Arms/Medication	Active Treatment: Fisetin 100 mg capsules (~20 mg/ kg/ day) will be administered orally for two consecutive days (days 1 and 2) followed by 28 days off. A second course will be given for two consecutive days (days 31 and 32) Placebo Control: Appearance matched capsule p.o. dose to match the number of capsules as if subjects were receiving active treatment. Placebo capsules will be administered orally for two consecutive days (days 1 and 2) followed by 28 days off. A second course will be given for two consecutive days (days 31 and 32)
Blinding Procedure:	The block randomization chart will be securely kept by an Unblinded Study Team member and at the Vail Hospital Pharmacy (point of subject distribution). All study subjects and other Study Team members including the Principal Investigator will be blinded to treatment through 18 months follow-up. In addition, any individuals engaged by the Principal Investigator to provide and/or document assessment of study endpoints will be blinded to treatment.
Sample Size and Study Population:	A total of 100 male or female subjects 40-80 years of age will be recruited from a single clinical site, where the Principal Investigator conducts patient care.
Objectives:	Primary Objective

	
To evaluate as compared to placebo:
 
The safety of administering Fisetin in subjects with osteoarthritis (OA) of the knee.
 
Secondary Objectives
 
To evaluate as compared to placebo:
 
 1. Reduction of pro-inflammatory and cartilage degenerating SASP markers; 2. Improvement in physical function of the Study Knee; 3. Improvement in patient reported outcomes; 4. Improvement in the quality of articular cartilage in the Study Knee with quantitative magnetic resonance imaging (MRI); 5. Reduction in time to conversion to alternative treatment.

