6.1 Blinding

Blinding will be maintained through study follow-up until the last subject has been seen at 18- months and data has been analyzed. All study subjects and Study Team members responsible for subject evaluation, data management and analysis (including the Principal Investigator) will be blinded. In addition, any individual engaged by the Principal Investigator to provide radiographic, laboratory testing and and/or verification of data will be blinded to treatment.

Those unblinded include the Group Allocation Manager (not a member of the Study Team) that will be responsible for maintaining group assignment. In addition, the pharmacist responsible for medication distribution (including their team) will maintain a similar log and need to be unblinded to distribute study medication accurately.

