15.2 Study Design

The study will follow a two-arm, double-blind, placebo-controlled approach. Allocation will be 1:1 between the two groups. Study subjects, treating physicians, medical assistants, and other members in the research team who conduct subject contact and/or data analysis will remain blinded throughout the study period.

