15.3 Randomization

To better ensure equivalent group sizes in the event of unenrollment or loss-to-follow-up, a block randomization scheme will be followed with block size of $n=8$. The following steps will be adhered to when enrolling a subject into one of the two study arms:

1. Eight tokens, numbered 1-8, will be held in a jar stored in the study manager's office within TSC and SPRI.
2. Upon enrollment, a token will be drawn from the jar, and not replaced back into the jar.
3. The Block Number and Within-Block Number will be recorded by the study team on a blinded version of the Enrollment/Randomization log.
4. The Block Number and Within-Block Number will be disclosed to the Vail Health Hospital Pharmacy who will arrange the proper medication and record the subject onto an unblinded version of the Enrollment/Randomization log.

-
- When final token is taken from jar, enrollment within that block is complete, and all 8 tokens will be placed back in the jar in preparation for the next subject and the new block.

Figure 15.3 Portion of the randomization/enrollment log demonstrating group allocation for subjects enrolled into block #1.

Block Number	Within-Block Number	Group (Randomization not finalized, for illustration only)	Subject ID
		Patient	
		Enrollment	
		Date	
1	1	Fisetin	1
	2	Placebo	2
	3	Placebo	3
	4	Fisetin	4
	5	Placebo	5
	6	Fisetin	6
	7	Fisetin	7
	8	Placebo	8

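### Section 18.8.1 has the Study Team state the randomization group on the prescription, which is inconsistent with the blinding rules in 6.1 and the code-only process in 15.3; the label has no specified masked name

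*Combined protocol and SAP*

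**What the plan says.** On the prescription, 18.8.1 reads: "A prescription will be provided by the Study Team to the pharmacy indicating the appropriate randomization group and the number of pills to dispense". In the same section, the listed label elements begin "Protocol IRB #, PI Name, Name of Study Medication, Directions".

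On the blind, 6.1 states: "All study subjects and Study Team members responsible for subject evaluation, data management and analysis (including the Principal Investigator) will be blinded". Section 15.2 extends this to treating physicians and medical assistants, and adds that "other members in the research team who conduct subject contact and/or data analysis will remain blinded throughout the study period".

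On what the team handles, 15.3 says "The Block Number and Within-Block Number will be recorded by the study team on a blinded version of the Enrollment/Randomization log", and then "The Block Number and Within-Block Number will be disclosed to the Vail Health Hospital Pharmacy who will arrange the proper medication". The pharmacy enters the subject on its own unblinded log. The synopsis, Section 6.0 and Section 10.1 describe the same step as a Study Team member giving the pharmacist a randomization code. Section 18.8.2 tracks a randomization code on the pharmacy's sheet.

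On who may know the arm, the documents differ. The synopsis says "The block randomization chart will be securely kept by an Unblinded Study Team member and at the Vail Hospital Pharmacy", while 6.1 says "Those unblinded include the Group Allocation Manager (not a member of the Study Team"), together with the pharmacist and the pharmacy team.

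**The concern.** A person can write the group on a prescription only if that person knows the group. The rest of the plan is built so that the study team does not know it: the team draws a token, records a number and passes the number on, and only the pharmacy's list turns it into an arm. Section 18.8.1 runs the other way, with the team telling the pharmacy the group.

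The primary endpoint is most exposed. Section 15.5.1 compares adverse events by relatedness, severity and expectedness, among other things. The Principal Investigator judges relatedness (12.2.3) and confirms severity (12.3.1). Knowledge of the arm could shift those judgements without anyone intending it. The pain scale and the questionnaires are self-reported, and the walking, stair and strength tests depend on effort, so they too are open to influence from staff or subjects who know the arm. Serum markers and MRI relaxometry are less exposed.

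The label raises a lesser question of the same kind. The first dose is taken at the clinic (10.1), later doses are self-administered, and drug is returned at Visit 4 (Appendix B), when adverse events and questionnaires are also collected. A label that named the contents would be seen by both subjects and staff.

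**Working it through.** The point rests on no alpha, power, effect size or dropout figure, and the plan gives no number to reproduce. The check is a comparison of passages.

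**1. What group means.** In the log shown as Figure 15.3, the Group column contains fisetin or placebo and is separate from the block and within-block columns. Section 12.3.1 treats disclosure of group identity as unblinding. In the plan's own usage, then, the group is the arm and not the code.

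**2. What crosses from team to pharmacy.**

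| Section | Item passed on or tracked | Reveals the arm to the team? |
|---|---|---|
| 15.3 | Block and within-block number | No |
| Synopsis, 6.0, 10.1 | Randomization code | No |
| 18.8.2 (pharmacy sheet) | Randomization code | No |
| 18.8.1 | Randomization group and pill count | Group: yes. Count: no |

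The pill count is harmless because 7.4.1 gives the placebo arm the same number of capsules per day as if fisetin were being taken. Only the group entry in 18.8.1 is out of line.

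**3. Who could write the prescription without breaking the blind.** Section 18.8.1 says only that the Study Team provides it. There are three cases.

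- The writer is a blinded member and group means the arm. Under 15.3 this person holds no arm to write. Either the instruction cannot be followed, or the arm must first be disclosed to the writer, who is then unblinded.
- The writer is the unblinded Study Team member of the synopsis. No blind is broken. But 6.1 provides for no such person, since its allocation manager is outside the Study Team, and 15.2 would require that the person have no subject contact and no part in data analysis.
- Group is loose wording for the code. No blind is broken, but the sentence does not say what it means.

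Section 18.8.1 does not say which case applies.

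**4. Label.** Section 6.0 defines Study Medication as the collective term for fisetin and placebo. Read with that definition, the label element could be one common name. Read as the name of the product in the bottle, it would identify the arm. No section specifies the printed name or says that it is masked.

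**5. Allocation concealment, under the first case only.** Section 15.3 fixes the block size at 8 with 1:1 allocation, and Figure 15.3 illustrates 4 per arm. Assume that every block is 4:4 and that the person enrolling subjects knows all earlier arms in the block. The expected number of correct best guesses per block is then

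4 + (2^8 / C(8,4) − 1)/2 = 4 + (256/70 − 1)/2 = 4 + (3.657 − 1)/2 = 5.33,

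against 4 of 8 by chance, and the last assignment in each block is certain. This shows what literal compliance would put at risk. It does not estimate what will happen.

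**The case against.** The strongest reply is that the plan, taken as a whole, describes a code-based process held by the pharmacy. The synopsis and Sections 6.0, 10.1, 15.3 and 18.8.2 agree on this, so the one phrase in 18.8.1 is most plausibly loose wording. A blinded member has no arm to write down, so in practice either the code is written or the unblinded member writes the prescription, and neither breaches the blind. Section 6.1 blinds Study Team members by responsibility, not every member without exception, and the synopsis expressly provides for one who is unblinded. Section 12.3.1 also speaks of a team member who can disclose the group in an emergency. On the label, Study Medication is a defined collective term, the capsules are matched in appearance, and 7.3 refers to pharmacy operating procedures that are not part of these documents.

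Much of this stands. A reader might infer that following 18.8.1 must break the blind, or that the label will name the arm. The documents support neither inference. The first fails because the synopsis supplies a person who could write the group without a breach. The second fails because the label wording fits a common name and contradicts nothing in 6.1 or 15.3.

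The reply does not remove the inconsistency. Section 18.8.1 does not restrict the task to an unblinded person, it uses a word that elsewhere means the arm, and the synopsis and 6.1 disagree on whether the person holding the allocation record belongs to the Study Team. Procedures held at the pharmacy cannot settle what the Study Team is told to write.

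**Conclusion.** The prescription sentence in 18.8.1 is wrong as written. It is inconsistent with 6.1 and with the code-only process described elsewhere. Followed literally, it would unblind any Study Team member who writes the prescription, unless that person is the unblinded member of the synopsis, whom 6.1 does not recognise. The label is a gap: masked wording is not specified, but no break follows from the text.

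The instruction reaches every dispensing, so every randomized subject falls under it. That is the reach of the rule. It should not be read as a finding that any subject or assessor will be unblinded. There is no effect on sample size or power, and the size of any bias in adverse event attribution or in self-reported and effort-dependent outcomes cannot be derived from the documents.

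The conclusion assumes that group in 18.8.1 has the meaning it has in Figure 15.3 and 12.3.1. If it means the code, what remains is a wording error, and the same correction removes it. The change should be made because it is nearly free and protects the primary endpoint. Confidence is medium, since actual practice may already follow 15.3.

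**What to change.** 1. In 18.8.1, have the prescription carry only subject ID, block and within-block number (or randomization code) and number of capsules. Remove the randomization group.
2. In 18.8.1, specify one masked product name, printed identically on the label for both arms.
3. Align the synopsis and 6.1 on who is unblinded outside the pharmacy, and on whether that person belongs to the Study Team. If so, state that the person has no part in subject contact, evaluation, data management or analysis, in keeping with 6.1 and 15.2. State that the arm is held only by the pharmacy and this designated allocation holder, and make the emergency disclosure in 12.3.1 run through them. Confining the arm to the pharmacy log alone would conflict with both the synopsis and 6.1, which place an allocation record with a second unblinded person.
4. If any subject has already been dispensed drug, check the prescription forms and labels used, and record whether any blinded person saw the arm.

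The cost is a few sentences in 18.8.1, the synopsis and 6.1, a prescription form and a label template, submitted as an amendment under 18.7. Dose, sample size, schedule and analysis are unchanged.

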18.8.2 Accountability

A medication tracking sheet will be kept by the Vail Health Hospital Pharmacy, which is to include the lot number, expiration date: date Vail Health Hospital Pharmacy received from Vital Nutrients, name of person receiving, date dispensed, name of person dispensing, randomization code, subject initials, number of capsules dispensed, date and number of returned capsules, name of person receiving, date and number discarded and by whom the capsules were discarded.

18.8.3 Disposition of Unused Study Medication

All unused, not previously dispensed Study Medication will be returned to the Study Sponsor for proper disposal or reallocation.

1. For remaining previously dispensed Study Medication, the label (including identifiable information) is taken off of the bottle and discarded in a shred bin by Vail Health Pharmacy;
2. Any remaining previously dispensed Study Medication is discarded in a secure biohazard bin by Vail Health Pharmacy;
3. Unused Study Medication that was not dispensed will be returned to the Study Sponsor to be stored or reallocated until the Study Medication expires. Upon expiration, the Study Medication will then be discarded in a secure biohazard bin.
4. Biohazard is picked up for disposal on a weekly basis.

18.9 Laboratory Qualification

All available information regarding laboratory qualification name and a copy of the medical license for laboratory directors, current normal ranges for the laboratory and proof of appropriate laboratory certification as appropriate will be maintained in the regulatory binders.

20.0 Declaration of Helsinki

The study will be conducted according to the guidelines established in the Declaration of Helsinki (World Medical Association 1964), Good Clinical Practices (GCPs) and local ethical and legal requirements. Subjects will be free to withdraw from the study at any stage without prejudice to their subsequent treatment.

22.2 Appendix B – Study Schemata

Visit Type	Screening	Baseline (4)	Emailed patient questionnaires	Safety Blood Draw	Phone Calls	Study Visit	Study Visit	Study Visit	Emailed patient questionnaires	Unscheduled
Clinic Visit Number	1	2		3		4	5	6		
Visit Date			Every 3 days for 6 wks after first dose of study drug and weekly for 6 wks thereafter	2 weeks after first dose of study drug	3 times after first dose of study drug	2 weeks after last dose of study drug	6 months after first dose of study drug	12 months from first dose of study drug	18 months after first dose of study drug	As needed for AEs/SAEs
Acceptable Visit Window		within 3 months of screening	± 1 day	± 2 days		± 10 days	± 4 weeks	± 4 weeks	± 4 weeks	N/A
Procedures & Assessments										
Informed Consent (1)	X									
Randomization (Placebo or Fisetin) (5)	X	X								
Medical/Surgical History & Demographics	X									
Physical Exam with Range of Motion of Study Knee	X					X	X	X		X
Vitals	X	X				X	X	X		X
BMI	X									
Record concomitant medications & supplements	X	X				X	X	X		X
Blood Draw (6)	X	X		X		X	X	X		X
Urine pregnancy test for WOCBP (2)	X	X								
PRO questionnaires			X			X	X	X	X	
Radiograph of Study Knee (3)	X									
Quantitative MRI		X					X	X		
Biomotion tests (functional performance, joint range of motion, muscle strength, video motion analysis)	X	X					X	X		
Dispense study drug		X								
Provide study drug diary		X								
Return study drug and diary						X				
Review and Assess AEs and SAEs				X	X	X	X	X		X

FOOTNOTES:

(1) Informed consent must be signed by the patient prior to ANY research-related procedures. The informed consent document can only be signed by the study PI and/or the treating clinician (MD/NP/PA) who is on the protocol.
(2) WOCBP = Women of Child Bearing Potential
(3) To confirm the presence of Kellgren-Lawrence grade II-IV OA.
(4) Procedures at Baseline may be performed at the Screening Visit after the Informed Consent Form (ICF) is signed.
(5) Randomization can occur at Screening or Baseline as long as the ICF has been signed and patient eligibility in the study is confirmed.
(6) If the Baseline visit occurs greater than 3 months after the Screening Visit, blood should be collected again for safety purposes.

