	
 3. Vital signs; 4. Medical and surgical history; 5. Demographic information; 6. Details of injury; 7. Severity of injury; 8. Medications; 9. Physical exam with range of motion (ROM) of the target limb; 10. BMI; 11. Urine pregnancy test for Women of Child Bearing Potential (WOCBP); 12. Blood analysis; 13. Completion of augmented PROs, including: NRS, IKDC, Lysholm, TEGNER, WOMAC and SF-12; 14. A radiograph of the target knee will be performed to confirm the presence of Kellgren-Lawrence grade II-IV OA; 15. The patients' medical record will be reviewed, and the subject will be interviewed to determine if inclusion/exclusion criteria are met; 16. Randomization. 
Patients who have met all eligibility criteria will be assigned, 1:1 via block randomization, to one of the two blinded study groups.
 
Visit 2 (Baseline) (Within 3 months of Visit 1)
 
Some procedures performed in this visit may be performed in Visit 1 provided that Informed Consent has been signed.
 
 1. Urine pregnancy test for Women of Child Bearing Potential (WOCBP) 2. Quantitative MRI; 3. Kinematic movement; 4. Assessment of muscle strength, isokinetic dynamometry; 5. Functional performance testing.
--	---

	
After randomization is performed, a Study Team member will then inform the Vail Hospital pharmacist of the subject's assigned randomization code the study medication will be obtained. The subject will take the first dose of study medication at the clinic.
 
Subjects will be instructed to self-medicate for day 2 followed by 28 days off. They will be instructed to begin a second course of treatment for two consecutive days (days 31 and 32).
 
Subjects will be reminded at Visit 3 in-person and over the phone 2-4 days prior to the last dosing of study medication about their upcoming dosing. If applicable, they will also be reminded to withhold current medications as instructed by the PI.
 
A Medication Log recording medication administration will be provided to the subject with instructions to complete during the period of administration.

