9.1 Enrollment Criteria

9.1.1 Inclusion Criteria

Subjects will be included if all of the following criteria are met:

1. Are male or female, ages 40-80;
2. Are willing to comply with all study related procedures and assessments;
3. Are ambulatory as defined by ability to complete functional performance testing;
4. Radiographic evidence of Kellgren-Lawrence grade II-IV osteoarthritis in one or both knees;
5. Scores 4-10 on the Numerical Rating Scale (NRS) for pain;
6. Stable dose of screening/baseline medications for at least 2 months prior to the anticipated date of study drug dosing.

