10.0 Study Visits

A full Study Schemata is provided in **Section 23.1** of this document.

Visit 1 (Screening/Enrollment)

At the first patient visit, the following procedures will be performed:

1. Full explanation of the clinical study, execution of Informed Consent, copy of signed informed consent sent home with patient;
2. Subject will be assigned a deidentified study number;
3. Vital signs;
4. Medical and surgical history;
5. Demographic information;
6. Details of injury;
7. Severity of injury;
8. Medications;
9. Physical exam with ROM of target limb;
10. BMI;
11. Urine pregnancy test for pre-menopausal women;
12. Blood analysis;
13. A radiograph of the target knee will be performed to confirm the presence of Kellgren-Lawrence grade II-IV OA;
14. The patients' record will be reviewed, and the subject will be interviewed to determine if the eligibility criteria are met;
15. Randomization.

Patients who have met all eligibility criteria will be assigned, 1:1 via block randomization, to one of the two blinded study groups.

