11.5 Patient Reported Outcomes (PROs): (Visits 1, 2, 4, 5, 6)

All PROs may be completed either on paper documents or by online questionnaire administration conducted via formsite (Vroman Systems, Inc.). Patients may complete questionnaires on a variety of electronic devices (personal computer, mobile phone, tablet).

PRO data to be collected include:

Augmented Numerical Rating Scale (NRS) (visit 2): At baseline then once every 3 days during FIRST 6 weeks of study medication treatment then once a week for an ADDITIONAL 6 weeks.

IKDC, Lysholm, TEGNER, WOMAC and SF-12 (visit 2, visits 4, 5, and 6 and remote assessments at 3- and 18-months post completion of medication).

The Numerical Rating Scale is a simple 0-10 self-reported severity of pain scale, (zero being no pain and 10 being the worst pain imaginable). This tool has been validated to provide excellent test-retest reliability in assessing knee pain associated with OA³¹. The Steadman Philippon Research Institute has added several stand-alone questions that are administered with the questionnaire. Only the validated portion, the simple NRS will be used to screen patients. In follow-up, each question will be analyzed individually. There is no composite score. A sample can be found in **Appendix C, Section 22.3** of this document.

The Lysholm knee scale is a condition-specific outcome measure that was originally designed to assess ligament injuries of the knee. It has been tested to provide excellent construct validity and overall acceptable psychometric performance for outcomes assessment of various chondral disorders of the knee. It is recommended that this tool be administered with additional psychometric measurements^{32,33}.

The TEGNER Activity Scale is a numerical scale ranging from 0 to 10. Each value indicates the ability to perform specific activities. An activity level of 10 corresponds to participation in the most physically demanding activities while a zero is assigned if a person is on sick leave or receiving a disability pension because of knee problems. It is simple to use, and it has been demonstrated to provide acceptable psychometric performances as outcome measures for patients with a meniscal injury of the knee. Like the Lysholm, it is recommended that it be used in conjunction with other psychometric tools such as the SF 12³².

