15.5.2.3 Pain and PRO Assessment

The hypothesis in this study is that FIS will induce a systemic anti-inflammatory and senolytic effect, thereby reducing pain and improving self-reported function and quality of life compared to the placebo group. Early subjective assessment (every 3 days for 6 weeks following the first dose of study medication and once weekly for the following 6 weeks) will be limited to a short augmented numerical rating scale questionnaire. Linear mixed-effect random-intercepts modeling will be used to characterize the trend in self-reported pain over 3 months, and to test whether treatment group is a significant predictor of pain reduction.

The IKDC, WOMAC, Tegner activity scale and Lysholm PRO measures will be administered at 2 weeks after the last dose of study medication and 6, 12, and 18 months following initiation of medication. For each time point, ANCOVA will be used with the subject's baseline PROM value used as a covariate. Among the 4 postoperative time-points for assessing these validated PROMs, the Holm-Bonferroni method will be used to control the family-wise type-1 error rate to 0.05 within each PROM scale tested. No multiplicity adjustments will be made across different PROMs, which are commonly highly intercorrelated.

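### Section 10 and Appendix B show no patient-reported outcome before dosing, while the Synopsis, Section 6 and Section 11.5 plan one at differing visits, so the ANCOVA baseline and the screening NRS may be missed

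*Combined protocol and SAP*

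**What the plan says.** Two parts of the plan depend on a PRO score taken before treatment.

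- Section 15.5.2.3, for IKDC, WOMAC, Tegner and Lysholm: "For each time point, ANCOVA will be used with the subject's baseline PROM value used as a covariate".
- Section 9.1.1, inclusion criterion 5: "Scores 4-10 on the Numerical Rating Scale (NRS) for pain". Section 11.5 confirms the tool: "Only the validated portion, the simple NRS will be used to screen patients".

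The sections that plan such a score do not agree on the visit. The Synopsis lists "Completion of augmented PROs, including: NRS, IKDC, Lysholm, TEGNER, WOMAC and SF-12" at Visit 1 and no PRO at Visit 2. Section 6 describes the questionnaires under Visit 2 and calls them the baseline assessment. The heading of Section 11.5 names Visits 1 and 2, but its text gives "IKDC, Lysholm, TEGNER, WOMAC and SF-12 (visit 2, visits 4, 5, and 6" for the five multi-item scales and Visit 2 alone for the NRS.

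The schedule itself has none. In Section 10 neither the Visit 1 list nor the Visit 2 list contains a PRO. In Appendix B the "PRO questionnaires" row is first marked in the emailed column, which starts after the first dose.

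**The concern.** Section 10 and Appendix B are what study staff would normally use as a checklist. If they are followed as written, the first clinic PRO is at Visit 4, after the last dose, and the first remote NRS also comes after dosing has begun. A pre-dose score cannot be recovered later.

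Three things are at stake. First, subjects without a baseline score cannot enter the planned ANCOVA unless the score is imputed, and Section 15.4 says that listwise deletion is to be avoided. Imputation under Section 15.7 could help if a few scores were missing, but not if nobody had one. Second, Section 10 places randomization at Visit 1 with no NRS listed, so a subject could be randomized before the qualifying score is on record. Third, Visit 2 may fall up to 3 months after Visit 1. If some subjects have a Visit 1 score, others a Visit 2 score and some both, the covariate has unequal lags and the analyst has to choose a definition that the plan does not supply.

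**Working it through.** **Step 1. The passages side by side.**

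| Place | Visit 1 (Screening) | Visit 2 (Baseline) |
|---|---|---|
| Synopsis | Full PRO set with NRS (item 13 of 16) | None |
| Section 6 | Not stated | Full PRO set with NRS |
| Section 11.5, heading | Yes | Yes |
| Section 11.5, text | Not named | NRS and the five other scales |
| Section 10, visit lists | None (15 items) | None (5 items) |
| Appendix B, PRO row | Blank | Blank |

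The Visit 1 lists in the Synopsis and Section 10 cover the same items in the same order, except that Section 10 lacks the PRO line: 16 − 1 = 15. Section 10 does list the check for the radiographic criterion, "A radiograph of the target knee will be performed to confirm the presence of Kellgren-Lawrence grade II-IV OA", but has no matching line for the NRS criterion.

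**Step 2. Is the blank in Appendix B an extraction fault?** Reading the row by column position gives: Screening blank, Baseline blank, emailed post-dose questionnaires X, Visit 3 blank, phone calls blank, Visits 4, 5 and 6 X, 18 months X, unscheduled blank. Other rows, such as the radiograph, MRI and dispensing, fall under their proper columns, and the separate lists in Section 10 show the same gap. The blank is in the plan.

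**Step 3. Do the footnotes cure it?** Footnote 4 lets Baseline procedures be done at Screening, but PROs are marked at neither visit. Footnote 5 requires confirmed eligibility before randomization, which presupposes an NRS score but does not schedule one. Footnote 6 repeats the blood draw after a long gap between visits and says nothing about PROs.

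**Step 4. Size, as illustration only.** The plan gives no figure for the PRO analyses. Its one sample-size figure, in Section 15.6, concerns T1rho. With 1.960 + 0.842 = 2.802, 2 × 2.802² / 0.73² = 29.5, which rounds up to the stated 30 per group. An exact t-test gives 30.4, that is 31. The 30 serves below only as a group size.

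Let ρ be the correlation between baseline and follow-up score. The documents give none, so 0.3, 0.5 and 0.7 are assumptions. ANCOVA leaves residual variance σ²(1 − ρ²), and an unadjusted comparison leaves σ². If the covariate were lost in every subject, the variance would rise by 1/(1 − ρ²):

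- ρ = 0.3: 1/0.91 = 1.10
- ρ = 0.5: 1/0.75 = 1.33
- ρ = 0.7: 1/0.51 = 1.96

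At 30 per group, 80% power and two-sided 0.05 before the Holm adjustment, the detectable standardized difference is 2.802 × √(2(1 − ρ²)/30). That is 0.69, 0.63 or 0.52 with ANCOVA, against 2.802 × √(2/30) = 0.72 without a baseline.

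**The case against.** The strongest reply is that a baseline is planned. The Synopsis, Section 6 and Section 11.5 all provide for PROs before dosing, Section 15.5.2.3 presupposes them, and this is a single-centre trial whose staff share one protocol. Section 11.5 says that the simple NRS is used for screening, and Section 10 requires record review and interview to establish eligibility. Any score from Visit 1 or Visit 2 precedes dosing and is usable as a covariate. The two visits may even coincide, because Visit 2 procedures can be done at Visit 1.

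All of this stands, and it rules out several stronger readings. A reader might infer that no baseline will be collected, that the ANCOVA cannot be run, or that inclusion criterion 5 cannot be documented. The documents do not support that: the items are missing from the lists and the schedule, not from the plan as a whole. A reader might also extend the ANCOVA consequence to every instrument. Section 15.5.2.3 names four scales. SF-12 is not among them, and the NRS is analysed by a random-intercepts model for which no baseline covariate is stated. Finally, the conflict does not show that Visit 2 must be the baseline. Visit 1, or the last value before dosing, would serve as well.

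What the reply does not remove is the contradiction. No rule says which section governs, and no section defines the baseline score.

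**Conclusion.** This is an internal inconsistency in the schedule and should be corrected. Section 10 and Appendix B show no PRO before dosing, and the sections that do plan one disagree on the visit. The baseline for IKDC, WOMAC, Tegner and Lysholm may be missed, the NRS for inclusion criterion 5 may be unrecorded at a Visit 1 randomization, and where both visits yield scores the baseline is undefined.

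The variance factors of 1.10 to 1.96 are a worst case. They assume loss of the covariate in every subject and correlations that the documents do not give. Partial loss or mixed timing would cost less, and mixed timing alone is a modest matter of precision. PROs are secondary endpoints: the primary endpoint is adverse events and the sample size rests on T1rho, so neither is affected.

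**What to change.** - In Section 10 and Appendix B, list the screening NRS at Visit 1, ahead of randomization.
- In the same two places, list the full PRO set at one named visit before the first dose.
- Align the Synopsis, Section 6 and both the heading and text of Section 11.5 with that choice, including the Section 11.5 line that ties the NRS to Visit 2 alone.
- In Section 15.5.2.3, define baseline as one pre-dose value, for example the last value before the first dose.

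The cost is schedule wording. The instruments are already planned, so no new questionnaire is needed. If subjects have already been dosed, check which pre-dose scores exist and report how many subjects lack one.
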